# **Study Protocol**

# **Study Design:**

The study is a parallel community-based 2-arm randomized controlled trial (RCT) in which the study evaluations will take place at the Center of Neurorehabilitation (CNR) at Sargent College, Boston University. We will enroll 44 community-dwelling adults ages 40-80 yrs with idiopathic PD of mild to moderate disease severity, who are independent community ambulators. We will exclude those with atypical PD, have significant freezing of gait, have history of falls in the past 3 months, have a comfortable walking speed <0.4 m/s, and significant cognitive or hearing impairments. Eligible participants will be randomly allocated to either

[figure not shown]

Figure 1 Study flow. Abbreviations: CoV: Coefficient of Variation; SAM: Step Activity Monitor; SRHI: Self-Report of Habit Index

Amped-PD (experimental arm) or Active Control (control arm). Assessments will include a standard set of motor and non- motor assessments and will be administered at Baseline, Post-Assessment (after 6 weeks of training), and Follow-up (after 2 additional weeks of unstructured training). Figure 1 summarizes the study flow for the protocol.

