  - iii. Quantification of movement will be performed using in-lab movement sensors (XSENS, Enschede, the Netherlands) and sensors of the music-based device (MedRhythms, Portland, ME) (see Appendix VII: Schematic of Wearable Sensors). These sensors will be used to measure gait quality during performance of the 10MWT and 6MWT as performed in the inperson screening, and to measure posture as examined in posture-related items within the UPDRS III and Mini BESTest. Sample metrics include but are not limited to gait velocity, stride length, cadence, and limb velocities, and postural sway measures based on velocity, magnitude, smoothness. As a clarification, the instrumented 10MWT and 6MWT as performed during the initial screen provide the data needed for this Baseline Assessment, therefore these tests will not be repeated.
  - iv. Functional Mobility will be measured via the Five Times Sit to Stand (5xSTS). The 5xSTS objectively assesses the time it takes to complete 5 sit-to-stands and is a method to observe movement strategies or compensations. The test will be performed in a standard chair with participants instructed to stand up and sit down 5 times as quickly as possible. The physical therapist conducting the test will be guarding the participant as necessary to optimize safety; however, if guarding is needed for the 5xSTS, participants will not be allowed to continue with the

intervention.

- Self-report/ Interview Measures:
  - i. Section I and II of the Movement Disorder Society Unified Parkinson Disease Rating Scale (MDS-UPDRS) will be utilized to assess non-motor and motor signs. Section IA includes 6 items related to non-motor experiences such as cognition, mood, and motivation which are assessed by the examiner. Section IB consists of 7 items related to non-motor aspects of experiences of daily living such as sleep and fatigue which are filled out by the participant (with or without the help of a caregiver), but independent of the examiner. Section II is a self-administered questionnaire consisting of 13 items related to motor aspects of experiences of daily living.
  - ii. The Self-Report Habit Index (SRHI) will be administered to measure exercise-habit strength and automaticity. This self-report index comprises of 12 statements with constructs spanning behavior repetition, automaticity, and identity, with responses made on 11-point Likert scales (0 = strongly disagree; 10 = strongly agree) (see Appendix VII: Outcome Measures).

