- iii. Self-Efficacy of Walking Duration (SEW-D) is a 10-item self-report that will be administered to determine participants' beliefs of their physical capabilities to successfully complete incremental 5-minute intervals (5 to 40 minutes) of walking at a moderately fast pace, with responses made on 11-point Likert scale (0% = not at all confident; 100% = highly confident).
- iv. Geriatric Depression Scale (GDS) is a brief, self-report involving yes/no questions instrument on psychological aspects and social consequences of depression in the elderly. The short form of GDS of 15-items will be used in this study.
- v. Health-related quality of life will be measured by the Parkinson's Disease Questionnaire 39 (PDQ-39)(see Appendix VII: Outcome Measures). The PDQ-39 is a self-report questionnaire that assesses quality of life over the past month across 8 different dimensions. Items are scored based on a 5-point ordinal system with lower scores reflecting better quality of life.
- Walking Activity:
  - Step Activity Monitor: Walking activity will be measured using the StepWatch 4 Activity Monitor (SAM; Orthocare Innovations, Mountlake Terrace, Washington). The SAM is a self-contained, maintenance-free device that combines acceleration, position and timing information to count complete gait cycles (strides) of the user. It is the size of a pager, weighs 38g (roughly the weight of two AA batteries for comparison) and will be attached with self- adhesive straps above the lateral malleolus (where the shin meets the foot) of the participants' less impaired lower extremity. Data from the SAM, which includes measurement of daily step counts and step intensities, will allow us to examine changes in physical activity in response to the intervention. The validity and reliability of the SAM for capturing stride counts has been demonstrated in persons with various neurological disorders including PD (Shepard 1999, Coleman

- 1999, Macko 2002, Salarian 2004, Gaines 2005, Manns 2009, Speelman 2011).

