- 1.cRandomization: At the completion of procedures for Baseline Assessment, the participant will be randomized to receive either the experimental or control arm of the intervention. The experimental arm, called Amped-PD, is a 6-week community-based structured walking program that uses a music-adaptive RAS followed by 2 weeks of unstructured walking protocol (continue as desired) for a total of 8 weeks. The control arm, called Active-Control is a similarly structured 6-week community-based walking program that does not use RAS, followed by 2 weeks of unstructured walking protocol (continue as desired) for a total of 8 weeks of training. Block randomization with balanced allocation between the two groups will be implemented. A randomization list will be generated prior to enrollment of participants. The researcher will gain knowledge of treatment assignment only after procedures in In- person Screen and Baseline Assessments have been completed.

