## **Statistical Analysis Plan**

We will use parametric statistics to data with normal distribution verified using Shapiro-Wilk test and to data that meet the assumptions of homogeneity of variances using Levene's test. Otherwise, non-parametric statistics will be used.

To examine between-group differences for all primary outcomes (moderate intensity minutes, daily steps, stride time variability, and habit strength), we will run a one-way ANOVA or Kruskall-Wallis test to compare change scores at the 6-Week and 8-Week clinical assessments relative to baseline.

To examine within-group differences for all primary outcomes (moderate intensity minutes, daily steps, stride time variability, and habit strength), we will run a Repeated Measures ANOVA or Friedman's ANOVA on absolute values of all primary outcomes across their respective timepoints, with multiple post-hoc comparisons corrected using Bonferroni adjustments.

For all secondary outcomes, we will perform between-group analyses using non-parametric statistics to compare change scores at the 6-Week and 8-Week clinical assessments relative to baseline, using two-tailed tests with alpha set at 0.05.

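### Primary outcomes: one baseline-adjusted model on a pre-named scale, with an estimate and confidence interval, would usually serve better than unadjusted change scores and a pre-test switch

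*SAP*

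**What the plan says.** The SAP (Statistical Analysis Plan) names four primary outcomes: moderate intensity minutes, daily steps, stride time variability and habit strength. For the comparison between arms, "we will run a one-way ANOVA or Kruskall-Wallis test to compare change scores at the 6-Week and 8-Week clinical assessments relative to baseline".

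The choice between the two tests is left to the data. Parametric methods are kept for outcomes that pass two checks, in the SAP's words "verified using Shapiro-Wilk test and to data that meet the assumptions of homogeneity of variances using Levene's test". If either check fails, the plan falls back on ranks: "Otherwise, non-parametric statistics will be used". The SAP gives no threshold for either pre-test. It does not say whether they run per arm, per timepoint or once per outcome. It names no between-group effect estimate and no confidence interval. A two-sided alpha of 0.05 is stated for the secondary outcomes only.

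On size, the Protocol (Study Design) says "We will enroll 44 community-dwelling adults ages 40-80 yrs with idiopathic PD" and gives no power calculation. On allocation (section 1.c), "Block randomization with balanced allocation between the two groups will be implemented". Baseline step monitoring, the habit index and the instrumented walk tests are all collected before training starts (First Evaluation Visit), so baseline values are available as covariates.

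**The concern.** Two features of the primary comparison invite improvement.

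- **Precision.** Subtracting baseline assumes that each unit of baseline carries over fully into follow-up. If the true slope is below 1, the change score carries baseline noise that an estimated slope would remove. With 44 participants that precision is worth having.
- **Effect measure.** ANOVA compares mean change. Kruskal-Wallis compares ranks and gives no estimate by itself. Because the pre-tests choose, nobody can say beforehand what a given primary result will measure. If the pre-tests run separately at each timepoint, the 6-week and 8-week results for one outcome could rest on different measures.

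**Working it through.** **Inputs.** From the documents: 44 participants with balanced allocation, taken as 22 per arm. Assumed, because the documents do not give them: correlation rho between baseline and follow-up of 0.3 to 0.9; follow-up SD equal to k times baseline SD, k from 0.8 to 1.5; two-sided alpha 0.05 for the primary outcomes; 80% power for the planned ANOVA on change. The plan has no power figure of its own to reproduce.

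**Formulas, baseline SD set to 1.**
- Variance of change: 1 + k² − 2·rho·k.
- ANCOVA residual variance: k²(1 − rho²).
- Cost of estimating the slope: 1 + 1/(44 − 4) = 1.025.
- Power with ANCOVA: Φ(2.80/√ratio − 1.96), where 2.80 = 1.96 + 0.84.

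Example, k = 1, rho = 0.5: change variance 1 + 1 − 1 = 1; ANCOVA variance 0.75; ratio 0.75 × 1.025 = 0.769; power Φ(2.80/0.877 − 1.96) = 89%.

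**Normal data: ANCOVA/change variance ratio, with power in brackets.**

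| k | rho 0.3 | rho 0.5 | rho 0.7 | rho 0.9 |
|---|---|---|---|---|
| 0.8 | 0.515 (97%) | 0.586 (96%) | 0.643 (94%) | 0.623 (94%) |
| 1.0 | 0.666 (93%) | 0.769 (89%) | 0.871 (85%) | 0.974 (81%) |
| 1.25 | 0.804 (88%) | 0.915 (83%) | 1.005 (80%) | 0.974 (81%) |
| 1.5 | 0.893 (84%) | 0.988 (80%) | 1.023 (79%) | 0.797 (88%) |

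With equal SDs, multiplying 44 by the ratio shows that about 29, 34, 38 and 43 participants under ANCOVA would match 44 under change scores. Before the slope cost the ratio cannot exceed 1, and it reaches 1 where the true slope k·rho is 1. The worst case is therefore 1.025. With 18 completers per arm it is 1 + 1/(36 − 4) = 1.031.

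**How often the pre-tests switch.** Take Shapiro-Wilk in each arm plus Levene, each at an assumed 0.05. With normal data and equal variances, 1 − 0.95³ = 14.3% of analyses go to Kruskal-Wallis by chance; simulation gave about 15%. At change-score skewness of 0.7 and 1.0 it gave 39% and 59%.

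**Whether the switch matters.** In 6,000 simulated trials per scenario (rho 0.6, effect 0.6 SD), ANOVA and Kruskal-Wallis disagreed at 0.05 in 7.2% of normal and 20.5% of log-normal trials. With no effect, the two-stage rule rejected in 5.3% (normal) and 4.9% (log-normal).

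**Skewed data: simulated power (%) at rho 0.5/0.7/0.9, multiplicative effect, 22 per arm.**

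| Distribution | Plan | Raw ANCOVA | Log ANCOVA | Rank ANCOVA |
|---|---|---|---|---|
| Log-normal, skewness 1.75 | 80/81/81 | 84/80/78 | 89/87/86 | 86/82/78 |
| Log-normal, skewness 3.7 | 88/88/89 | 83/81/79 | 95/94/94 | 93/91/88 |
| Gamma, skewness 1.75 | 78/76/80 | 84/78/81 | 74/70/72 | 77/72/71 |
| Gamma, skewness 2.24 | 74/73/77 | not run | 65/60/65 | 73/66/70 |

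The cells use 2,000 to 3,000 trials each, so Monte Carlo error is about 1 point. A further gamma run at skewness 1.75, in which the plan had 55–66% power, gave log ANCOVA 52–58% and rank ANCOVA 53–59%. With about 12% zeros the results conflict: one set-up gave rank ANCOVA 92/87/86% against 87/83/84% for the plan, and another gave 68/72/72% against 75/81/80%. With an additive effect in log-normal data of skewness 3.7 at rho 0.9, raw ANCOVA had 84% against 96% for the plan, a loss of 12 points.

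**The case against.** The strongest reply is that nothing here is broken. Change scores are unbiased under randomisation, and the pre-test rule held its type I error in simulation. The normal-data effect on power runs from −1 to +17 points on inputs that the documents do not supply. All of that stands.

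The second reply is that ANCOVA is not safely better when outcomes are skewed, and that stands too. Log ANCOVA wins in log-normal data because the log is the ideal scale there. With gamma data of the same skewness and a multiplicative effect it falls below the plan. A rule such as taking logs whenever an outcome is skewed and positive, and ranks whenever zeros occur, is tempting but not supported. The documents give neither the distributions nor the shape of the effect.

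Two other readings go too far. A reader might infer that pre-testing inflates false positives; the simulations show no material inflation. A reader might also infer that the method will differ between 6 and 8 weeks; that follows only if the pre-tests run per timepoint, which the SAP leaves open.

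None of this answers the reporting gap: the SAP still names no between-group estimate or interval, and it still lets the data choose the measure.

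**Conclusion.** The point holds as a low-cost improvement to a valid plan. For roughly normal outcomes, baseline adjustment is usually at least as precise. With equal SDs, 80% power becomes 93/89/85/81% at rho 0.3/0.5/0.7/0.9. There is no gain when the true slope is near 1, and the loss is at most 2.5% of variance. These figures rest on the assumed 22 per arm, alpha, power basis, correlations and SD ratios.

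For skewed outcomes no general gain can be claimed. In the simulations, log ANCOVA lost about 3 to 13 points to the plan with gamma data and a multiplicative effect. Rank ANCOVA could lose with many zeros, and raw ANCOVA lost up to 12 points in strongly skewed log-normal data.

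The case for naming one analysis, one scale and one effect measure per primary outcome does not depend on any of these power figures.

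**What to change.** For each primary outcome, replace the pre-test switch with one primary model: ANCOVA of the 6-week value, and separately of the 8-week value, on the baseline value and arm.

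- **Scale.** Name one scale per outcome and use it at both timepoints. Write it into the SAP before outcome data are examined by arm. That is a firmer anchor than unblinding, because section 1.c conceals allocation only until baseline assessment is complete and the Protocol describes no later masking. Choose from what is known about each measure, not by an automatic rule. The range of each outcome limits the options: minutes of moderate activity can be zero, so a plain log is unavailable; habit items are bounded, "with responses made on 11-point Likert scales (0 = strongly disagree; 10 = strongly agree"; a coefficient of variation, if that is how stride time variability is reported, is positive.
- **Inference.** Use HC2 robust standard errors with t on n − 3 degrees of freedom: 41 if all 44 are analysed, 33 with 18 completers per arm.
- **Reporting.** Give the adjusted difference, or the ratio on a log scale, with a 95% CI at each timepoint.
- **Sensitivity.** Keep the planned Kruskal-Wallis test on change scores. Leave the secondary analyses unchanged.

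The cost is SAP wording and one degree of freedom per model, with no new data. The SAP should also state the possible loss of power for skewed outcomes if the chosen scale fits poorly.

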# Active-Control Intervention: Remote Walking Program Description

(Prescribed walking program of 15 hours total over six weeks + concurrent use of SAM device 4 days during early training)

**Overview:** The Active-Control Intervention is similarly structured as Amped-PD Intervention, with the only exception of not using RAS/ music-based device. Participants will be instructed to complete five home/community-based walking sessions per week (one session/ day, 30 minutes in duration) for six weeks.

**Description of Walking Sessions:** Without using the music-based device, participants will conduct the walking sessions at their self-selected pace in a home/community environment. All other considerations as outlined above apply to this intervention.

**Duration of Walking Session:** Each individual walking session will be completed within a 30- minute timespan (i.e., should not be split up throughout the day. Participants will be asked to use their own wristwatch,

timer, or cellphone to monitor the time/ duration of walking session. Participants are allowed to rest as needed during the 30-minute training period.

**Walking program diary:** Participants will be asked to record in a study diary their schedule (dates and times) of walking, location, record of any falls they experience and any comments/issues they experience while performing the walking program.

**Safety Considerations:** Same as above as outlined in Amped-PD. **Physical therapy check-in call:** Same as above as outlined in Amped-PD. **Step Activity Monitoring:** Same as above as outlined in Amped-PD.

Interruptions in training: In the event of unavoidable interruptions in training, booster sessions may be implemented to promote treatment fidelity. For training interruptions that last up to 2 weeks, the participant will continue the program and receive booster sessions at 100% of the time missed. For training interruptions of greater than 2 weeks, the training will be restarted after a reasonable washout interval, as determined by the Principal Investigator (a licensed physical therapist). If training interruption resulted in permanent change in eligibility, the participant will be withdrawn from the study.

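### The plan tests each arm separately over time on all four primary outcomes and does not say that efficacy rests on the between-arm comparison

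*SAP*

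**What the plan says.** The second paragraph of the SAP compares the arms directly on each primary outcome (habit strength, stride time variability, daily steps and minutes at moderate intensity): "we will run a one-way ANOVA or Kruskall-Wallis test to compare change scores at the 6-Week and 8-Week clinical assessments relative to baseline".

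The third paragraph adds another analysis of the same four outcomes. Its purpose is given as "To examine within-group differences for all primary outcomes". The method is Repeated Measures or Friedman's ANOVA, carried out "on absolute values of all primary outcomes across their respective timepoints". Pairwise tests follow, "with multiple post-hoc comparisons corrected using Bonferroni adjustments". No arm term or arm-by-time term is named. The SAP does not write out that each arm is analysed separately, but this follows from the stated purpose and from the choice of Friedman's test, which has no between-group factor.

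The SAP does not rank the two analyses or call the second one descriptive or supportive. The significance level, "using two-tailed tests with alpha set at 0.05", appears only in the sentence on secondary outcomes.

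In the protocol, the Active-Control section gives the control arm the same programme apart from the music device: "Participants will be instructed to complete five home/community-based walking sessions per week", at 30 minutes per session for six weeks, as in the Amped-PD section.

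**The concern.** The trial asks whether music cueing adds to a walking programme. A within-arm test asks whether people in that arm changed. Because both arms are asked to walk more, change is plausible in both, and at 22 per arm a moderate true change will reach significance in some arms and miss it in others by chance. A report could then say that Amped-PD improved and control did not, on a primary outcome, when the arms do not differ. Nothing in the SAP rules that reading out. The only multiplicity correction in the SAP is attached to the within-group paragraph, which makes that paragraph look inferential.

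A second, smaller issue is missing data. Standard Repeated Measures ANOVA and Friedman's test use only participants with every timepoint. The SAP states no handling of missing data, and the protocol allows withdrawal after randomisation (Device Training; Interruptions in training).

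**Working it through.** The documents give no power, effect size, SD or dropout figure, so there is no stated result to reproduce.

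**Inputs from the documents.** 44 participants (Study Design) with balanced allocation (Randomization), taken as 44 / 2 = 22 per arm. Assessments at baseline, after 6 weeks and after 2 further weeks.

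**Assumptions.** Two-sided 0.05 for primary outcomes; three timepoints for every outcome (the step-monitor schedule has other wear windows); normal data; no dropout; within-person correlation 0.5, with 0.7 as a check; the same true change d in both arms at 6 and 8 weeks, in SDs of the outcome at one timepoint.

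**Formula.** If each within-arm test has power p and the true changes are equal, P(Amped-PD significant, control not) = p(1 − p). The maximum is 0.5 × 0.5 = 25%, at p = 0.5.

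**Simulation, correlation 0.5, 40,000 trials per row.** Column A: Amped-PD significant and control not, by Repeated Measures ANOVA. Column B: A, with the between-arm change-score tests at 6 and 8 weeks both non-significant. Column C: Amped-PD meets, and control does not meet, a stricter rule that also requires a baseline-to-6-week improvement at 0.05 / 3 (Bonferroni over three pairs).

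| d (SD) | p | p(1 − p) | A | B | C |
|---|---|---|---|---|---|
| 0 | 0.052 | 4.9% | 5.0% | 3.0% | 0.6% |
| 0.2 | 0.144 | 12.3% | 12.3% | 9.2% | 5.3% |
| 0.3 | 0.269 | 19.7% | 19.6% | 16.2% | 11.1% |
| 0.4 | 0.447 | 24.7% | 24.6% | 20.8% | 18.5% |
| 0.5 | 0.644 | 22.9% | 23.2% | 19.6% | 24.2% |
| 0.6 | 0.804 | 15.8% | 15.6% | 13.0% | 24.3% |
| 0.8 | 0.971 | 2.8% | 2.7% | 1.9% | 11.8% |

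The formula and the simulation agree. The Bonferroni step does not remove the pattern; it moves the peak to a larger true change.

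**Correlation 0.7.** Among the values tried, column A peaks at 24.4% and column B at 20.5%, both at d = 0.3. The peak is about the same height but comes at a smaller d, because the SD of change falls from √(2 × 0.5) = 1.00 to √(2 × 0.3) = 0.77.

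**Comparison.** In the same simulated trials the between-arm test at 6 weeks rejects in about 5%, and at least one of the 6- and 8-week tests rejects in about 9%.

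**Four outcomes.** If they were independent, the chance of at least one column B pattern at d = 0.4 would be 1 − (1 − 0.208)⁴ = 61%. Positive correlation between outcomes lowers this, and the documents give no correlation.

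**The case against.** The best reply is that the correct test is already planned, and comes first. The SAP's second paragraph compares the arms directly on all four outcomes, and the third says openly that it concerns within-group differences. This stands. A reader might infer that the plan lacks a between-arm test, or intends to claim efficacy from within-arm p-values. The documents support neither: no sentence infers a treatment effect from the within-group results. The gap is one of ranking and labelling, and harm would depend on how results are reported.

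Two stronger readings of the size also fail.

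- A reader might count trials in which either arm alone is significant and compound that over four outcomes, making the pattern look nearly certain. Counting either arm doubles p(1 − p) by including trials where only control improves. Compounding needs independent outcomes, but daily steps and step intensity come from the same step monitor.
- A reader might work out the daily steps that the prescription should add and conclude that within-arm significance is close to guaranteed. That is an upper bound. Rests are allowed within sessions, the phone screen admits people who already take 30-minute walks up to three times a week, and monitor wear after the first training week falls in the self-managed follow-up or after the final visit. The documents give no SD. A change that large would also make both arms significant, so the one-arm pattern would become rare.

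It can also be said that a single labelling sentence would cure the main problem. It would, but it would leave the complete-case per-arm tests in place.

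**Conclusion.** The concern holds as a matter of hierarchy and choice of analysis. The SAP plans unranked per-arm significance tests on every primary outcome, and these cannot answer the trial's question. With identical true change in both arms, the misleading pattern occurs in about 5% of trials per outcome when nothing changes, peaks near 25% at 0.4 SD (about 21% with both between-arm tests non-significant), and falls to about 3% at 0.8 SD. The chance over four outcomes is higher by an amount that depends on their correlation. These rates rest on the assumed effect sizes, correlation, three timepoints, alpha and absence of dropout; the loss from complete-case analysis is not quantified. The change is a worthwhile, inexpensive improvement and should be made before the data are analysed.

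**What to change.** Replace the within-group paragraph with one repeated-measures mixed model per primary outcome: arm, time and arm-by-time, both arms together, every randomised participant with any data, and a covariance structure named in advance. Where normality fails, add a rank-based or transformed sensitivity analysis, so that the plan's non-parametric fallback is not lost.

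Then state three things:

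- Efficacy claims rest only on the between-arm contrasts at 6 and 8 weeks, reported with 95% CIs.
- This model supersedes the change-score test in the second paragraph; or, if both are kept, which of the two governs.
- Within-arm changes are descriptive, given as model estimates with 95% CIs and no p-values.

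The cost is SAP wording and one model per outcome, with no new data or participants. The downside is that within-arm p-values are no longer reported.

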Physical therapy check-in call: During the baseline evaluation visit, the research team will ask the participant which time each week is preferred to have a check-in call. This phone call will last approximately 5-10 minutes to check on participant engagement in the walking program, and to provide guidance regarding any questions/concerns and/or any medical/ technical issues. If participants are unable to carry out the walking program 5- days per week, a study staff member will discuss the barriers to implementation (by phone) and suggest ways to optimize adherence to the program (e.g., setting a schedule). A study staff member will also inquire about adverse events during the weekly phone call and ensure that the participant is comfortable with the walking program.

Step Activity Monitoring: After completing 4 days of wear prior to starting training, the participant will continue to wear the SAM for an additional 7 days upon intervention initiation (total of 11 days continuous wear). During training, both the SAM and the shoe sensors of the music-based device can be worn simultaneously on the same side of the body without interfering with a participant's walking and/or increasing the risk for trips/falls. Participants will return the SAM to study personnel via a pre-labeled, addressed envelope to mail following 11 days of continuous monitoring period. The researchers will download the data and will store in a secure server.

Interruptions in training: In the event of unavoidable interruptions in training, booster sessions may be implemented to promote treatment fidelity. For training interruptions that last up to 2 weeks, the participant will continue the program and receive booster sessions at 100% of the time missed. For training interruptions of greater than 2 weeks, the training will be restarted after a reasonable washout interval, as determined by the Principal Investigator (a licensed physical therapist). If training interruption resulted in permanent change in eligibility, the participant will be withdrawn from the study.

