# 3. Second Evaluation Visit: Post-Assessment Visit (approximately 2-3 hours):

The post-intervention assessment visit will be scheduled within approximately 7 days of completion of the structured walking program and take place at the Center for Neurorehabilitation at Boston University. This visit will entail the same battery of assessments performed at Baseline Assessment including: 10MWT, 6MWT, Borg's RPE, Mini BESTest, MDS-UPDRS I/II/III, 5xSTS, PDQ-39, SRHI, GDS. Quantification of movement will be performed using wearable sensors to measure balance and walking as examined in the aforementioned battery of assessments.

Further, a usability questionnaire will be administered for those who completed Amped-PD. For both Amped-PD and Active-Control groups, participants will be asked to bring in their study diary for study personnel to review and to make a copy for their data file. This study diary will be returned to the participant for continued use if needed during the Follow-up Period. For the Amped-PD group, they will have continued access to the music-based device during the Follow-up Period. The SAM monitor will be given to the participant to wear for 7 days during Follow-Up Training. Participants who withdraw or are withdrawn prior to completing their last walking session may be asked to complete closing visit activities, if feasible.

4. Follow-Up Walking Program (2 weeks): Extended Remote Walking Program

Description for both groups (recommended continuation of routine walking + concurrent use of SAM device 4 days during follow-up training)

**Overview:** Participants in both Amped-PD and Active-Control groups will be recommended to carry out the walking program independently for another 2 weeks,

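### The named repeated-measures and change-score tests drop, outcome by outcome, anyone missing a required value; one mixed model per primary outcome would keep the observed data, with a real but limited gain.

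*SAP*

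**What the plan says.** The SAP has two analyses for the four primary outcomes (moderate-intensity minutes, daily steps, stride time variability, habit strength).

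- **Between arms:** one-way ANOVA or Kruskal-Wallis to "compare change scores at the 6-Week and 8-Week clinical assessments relative to baseline".
- **Within arm:** Repeated Measures ANOVA or Friedman's ANOVA "on absolute values of all primary outcomes across their respective timepoints", with Bonferroni-corrected post-hoc comparisons.

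The SAP text names no analysis population, imputation, mixed model or missing-data sensitivity analysis. It does not list the timepoints of each outcome.

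The protocol foresees gaps:

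- People who leave before their last walking session "may be asked to complete closing visit activities, if feasible" (section 3, Post-Assessment Visit).
- Activity data come from a self-worn monitor sent back by mail: "Participants will return the SAM to study personnel via a pre-labeled, addressed envelope" (section 2, Step Activity Monitoring).
- Training may stop after a fall (Safety Considerations), and participants may be withdrawn after an interruption (Interruptions in training).
- Two exits can arise only in the Amped-PD arm, at device training after randomisation: needing another person's help while using the device, and being unable to operate it alone (section 1.d).

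**The concern.** Classical Repeated Measures ANOVA and Friedman's test need a full row per person. One missing timepoint removes that person's other values from the same analysis. A change score needs only its own two values, so the 8-week test makes no use of what a week-8 absentee showed at week 6.

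Two things are at stake. The first is precision, in a trial of about 22 per arm. The second is the 8-week randomised contrast: if the people who miss week 8 in one arm are those who were doing badly at week 6, the completers in that arm look better than the arm as randomised. The information needed to correct for this has been collected, but the named test cannot use it.

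**Working it through.** **Inputs from the documents.** Enrolment: "We will enroll 44 community-dwelling adults ages 40-80 yrs with idiopathic PD" (Study Design). Allocation: "Block randomization with balanced allocation between the two groups will be implemented" (section 1.c), read as 1:1, so 44 / 2 = 22 per arm. The 44 cannot be reproduced, because no effect size, SD, power or dropout allowance is given. No missing-data rate is given either, so every rate below is an assumption.

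**Step 1: which missing value affects which analysis.**

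| Missing item | Lost from | Not lost from |
|---|---|---|
| Week-8 visit | 8-week change test and within-arm analysis of stride time variability and habit strength | 6-week change test |
| One post-baseline monitor window | Within-arm analysis of minutes and steps, plus any change test using that window | Stride time variability, habit strength |

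**Step 2: complete rows per arm.** If each post-baseline value is lost independently with probability q and k values are needed, expected complete rows = 22 × (1 − q)^k, with baseline taken as complete.

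| q | k = 2 | k = 3 |
|---|---|---|
| 5% | 22 × 0.9025 = 19.9 | 22 × 0.8574 = 18.9 |
| 10% | 22 × 0.81 = 17.8 | 22 × 0.729 = 16.0 |
| 15% | 22 × 0.7225 = 15.9 | 22 × 0.6141 = 13.5 |

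Here k = 2 is the 6- and 8-week visits. k = 3 is the largest reading for the monitor: first week of training, follow-up training, and the days after the final visit.

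**Step 3: bias when week-8 loss depends on the observed 6-week change.** Simulation with 22 per arm, 8,000 trials per scenario and a true 8-week difference of 0.30 SD. Visit correlations are 0.60 (baseline with each later visit) and 0.75 (weeks 6 and 8). In one arm the log-odds of missing week 8 rise as the standardised 6-week change worsens (slope 1 or 1.5, base rate 10% or 20%). In the other arm loss is unrelated to response. About 14 to 27% of the affected arm misses week 8.

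- Completer estimate: averages 0.37 to 0.49.
- All-observed-data likelihood estimate: averages about 0.30.
- Variance of the latter: roughly 2 to 8% lower.

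A second pattern points the same way. With no true effect and a correlation of 0.7 between 6- and 8-week change, removing the worst 10%, 15% or 20% of one arm gives a completer bias of 0.14, 0.19 or 0.25 SD. Dropping the worst 2, 3 or 4 of 22 gives type I error of 7.3%, 9.3% or 11.7% at a nominal 5%. The bias of an estimate that keeps the 6-week data is about 0.00.

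**Step 4: the same set-up as the first simulation, but leavers lose both post-baseline values.** The all-observed-data estimate averages 0.35 to 0.44. Excess over the truth is 0.05 to 0.14, against 0.07 to 0.19 for completers. At the two ends, 0.05 / 0.07 = 71% and 0.14 / 0.19 = 74% of the bias remains.

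**Step 5: timepoints of the monitor outcomes.** The windows described are baseline (4 days), the start of training (7 days), follow-up training (7 days) and after the final visit (4 days). None is placed at the end of the six-week programme. The headings of the two intervention descriptions and of the follow-up programme say 4 days where the text says 7. A model with baseline, week 6 and week 8 therefore fits stride time variability and habit strength, but not yet the activity outcomes.

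**The case against.** **The SAP never prescribes a complete-case analysis, and change scores can be analysed after imputation.** True. The completer reading follows from the named tests plus silence on missing data. But a written policy that did not impute would still leave these tests discarding observed values, so the choice of method matters.

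**A reader might infer that one lost window or missed visit removes a randomised participant from the trial's results.** The documents do not support that. As Step 1 shows, the loss is confined to particular outcomes and analyses.

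**A reader might infer that a mixed model removes attrition bias in general.** It does not. The closing-activities sentence concerns people who leave before the last walking session, and the withdrawals described mostly arise during training or at device training. Many such leavers would have only a baseline value, and Step 4 then applies. This objection stands and limits the claim.

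**The protocol works to prevent gaps.** It provides a call 24 to 48 hours after the evaluation about the monitor, wear reminders, a removal log, weekly check-in calls and booster sessions. These may keep loss low. They do not change what the named tests do with the loss that remains.

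**Conclusion.** The point holds in limited form. As written, the Repeated Measures/Friedman analysis of an outcome drops anyone missing one of its timepoints, and the 8-week change-score test ignores the 6-week value of anyone missing week 8.

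A model on all observed values gives a small precision gain (roughly 2 to 8% lower variance). It also removes the bias that arises when week-8 loss depends on observed 6-week values (about 0.07 to 0.19 SD in the scenarios tried). It removes little of the bias from people who leave before any post-baseline value. If loss is unrelated to response, the gain is precision only.

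These sizes rest on assumed loss rates, correlations and dropout patterns, so they show what could happen and do not forecast this trial. The change is worth making because it is cheap, but the plan is not invalid without it.

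**What to change.** For each primary outcome, replace the Repeated Measures/Friedman analysis and the separate change-score tests with one linear mixed model.

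1. **Data:** all observed values of all randomised participants, as allocated.
2. **Model:** arm, time and arm-by-time, with unstructured covariance and Kenward-Roger degrees of freedom. Take both the between-arm differences in change and the within-arm changes from it.
3. **Timepoints:** baseline, 6 and 8 weeks for stride time variability and habit strength. For minutes and steps, use the actual monitor windows, after reconciling the 4-day and 7-day wear statements and naming which windows serve as the 6- and 8-week values.
4. **Skewness:** fix in advance how skewed outcomes are handled, rather than choosing after seeing the data.
5. **Sensitivity:** report the completer analysis, and a not-missing-at-random analysis that covers leavers with no post-baseline value.

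The cost is SAP wording and modest extra programming; no visit, procedure or treatment changes. The model relies on a missing-at-random assumption. That is weaker than what the completer analysis needs, but it is still an assumption, hence item 5.
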